3.2. Study Endpoints

The primary utilization and safety analyses of the inserters will be conducted at Day 7; safety analyses of the FAI insert will be conducted at Day 7 and Month 12. Analyses will be based on individual eyes.

Evaluation of Mk II inserter and Mk I inserter

Utilization evaluation (based on individual eye):

The primary utilization endpoint is defined as the proportion of intravitreal insertion procedures that are assessed by the Investigator as satisfactory. A satisfactory procedure is defined as one receiving a score from the Investigator as either Very Easy (VE), Easy (E), or Routine (R), according to the following categories:

- Very Easy (VE)
- Easy (E)
- Routine (R)
- Difficult (D)
- Very Difficult (VD)

Secondary utilization endpoints include:

- Clarity of the Instructions for Use, as assessed by the Investigator
- Differences between observed procedure and instructions for use, as assessed by an Observer

Safety evaluation (based on individual eye):

Safety will be evaluated over one period: Day 1- Day 7, and will include:

• Ocular adverse events, including: procedure-related adverse events, IOP increase/decrease, medications/procedures required to treat adverse events, clinically significant ocular changes

Evaluation of the FAI insert

Safety will be evaluated for two periods: through Day 7 and through Month 12. Descriptive statistics will be used to present the results of all safety evaluations and will include:

- Ocular adverse events (base on individual eye), including: IOP increase/decrease, medications/procedures required to control elevated/low IOP, development or worsening of cataract, cataract-related procedures, clinically significant ocular changes
- Systemic adverse events

4. General Statistical Considerations

Continuous data will be described using descriptive statistics (i.e. n, mean, standard deviation, median, minimum, and maximum). Categorical data will be described using the eye/subject count and percentage in each category. For the summary statistics of all numerical variables unless otherwise specified, minimum and maximum will be displayed to the same level of precision as reported. Mean and median will be displayed to one level of precision greater than the data collected. Standard deviation / standard error will be displayed to two levels of precision greater than the data collected. P-values will be rounded to three decimal places. If a p-value is less than 0.001 it will be reported as "<0.001". If a p-value is greater than 0.999 it will be reported as ">0.999".

Data will be displayed in all listings sorted by treatment group, unless otherwise specified. A subject will be assigned by the study site. The first 3 digits of the ID number will be the assigned site number, followed by a 3-digit subject number in sequential order (i.e., 201001, etc.). Within the IWRS system, at the time of randomization, a 1-digit eye identification number will be added: the subject's first eye (if eligible) to be randomized will be assigned the additional digit "1" (e.g., 201001-1); the subject's second eye (if eligible) to be randomized will be assigned the additional digit "2" (e.g., 201001-2). However all data within the clinical data base will be recorded based on the subject number (without the eye id) and eye level data will be recorded as OD or OS. For non-ocular/systemic assessments, subjects who have more than one eye randomized/treated will have data listed once for each different treatment received. (e.g., the data could be listed for both the Mk II and Mk I injectors.)

When count data are presented, the percentage will be suppressed when the count is zero in order to draw attention to the non-zero counts. A row denoted "Missing" will be included in count tabulations where specified on the shells to account for dropouts and missing values. For by treatment summaries, the denominator for percentages will be the number of eyes in each category in that treatment within the analysis population of interest, unless otherwise specified. For summaries for all subjects for data summarized at the subject level, the denominator for percentages will be the number of subjects who have at least one eye within the analysis population of interest, unless otherwise specified.

Unless otherwise specified, baseline will be defined as the last non-missing evaluation prior to or on the date of treatment injection (Day 1). The study day will be calculated as assessment date – date of treatment injection (Day 1) + 1. Study day for non-ocular events and assessments will be determined using the date of treatment in the first treated study eye. Study day for ocular assessments for the first treated eye will be determined using the date of treatment in the first treated study eye. If the second eye is also treated, study day for the ocular assessments in that eye will be based on the date of treatment in that eye. If the second eye is not treated, study day for ocular assessments in that eye will be based on the date of treatment in the treated study eye.

For all utilization and safety analyses, analysis visit windows will be used for assigning assessments to an analysis visit, as follows:

Scheduled Visit	Target Day	Visit Window (Days)		
Screening	-60 to 0	Not applicable		

Day 1	1	Not applicable
Day 7	7	4 to 10
Day 28	28	14 to 42
Month 3	90	69 to 111
Month 12	360	332 to 388

Only those assessments which are assigned to an analysis visit will be included in the summary tables and figures which are presented by visit. If there are multiple assessments assigned to the same visit window, the observation to be used for analysis will be determined as follows:

If there is only one observation falling into a defined visit window, then that observation will be flagged for inclusion in by-visit analyses.

If there is more than one observation falling in a defined visit window and one of the observations was made in a "scheduled" study visit (e.g., day 7, day 28, Month 3, etc.) and the other observation(s) was made in an unscheduled visit, then the observation from the scheduled study visit will be used for by-visit analyses.

If there is more than one observation falling into a defined visit window and all observations are from unscheduled visits, then the earliest observation with non-missing data for a given assessment will be used for by-visit analyses.

All assessments will be presented in the data listings.

The Day 7 analysis will include all assessments with a start day on or before the upper limit of the Day 7 visit window (study day 10). The analysis at Month 12 will include all data in the database.

Subjects may have more than one eye randomized to treatment; therefore, for summaries counting patients by treated eye, a subject may be included more than once in a given summary. The same subject may be included more than once in the same treatment group if both eyes are randomized to the same inserter. Similarly, a subject may be counted more than once in the total eyes column if both eyes are randomized.

Subjects will be counted at most once for total subject summaries even if the subject has both eyes randomized.

Eyes not receiving assigned treatment and non-study eyes will have all safety data listed and will be included in selected AE and SAE summaries only. In the listings, randomized eyes that did not receive treatment will be grouped separately by their randomized treatment assignment (i.e., Mk I inserter - Not Treated, Mk II inserter - Not Treated). Non-randomized eyes which do not receive treatment will be grouped in listings. Percentages for Safety population summaries will be based on the number of eyes that received treatment.

All analyses will be conducted using SAS Version 9.2 or higher.

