9.7.1. Designation of Study Eye and Randomization

For subjects with unilateral uveitis, the study eye will be the affected eye.

For subjects with bilateral uveitis, the study eye(s) will be the eye(s) meeting eligibility criteria. If both eyes satisfy eligibility criteria, both eyes may be enrolled in the study. In a subject with both eyes eligible for enrollment, randomization of the subject's second study eye may occur no sooner than the study Day 7 visit of that subject's first study eye, and no later than the last day of the study Day 7 visit window of that subject's first study eye.

If the subject's eye meets the inclusion and exclusion criteria at Screening and Day 1, randomization will be performed via the IWRS. Randomization will be stratified on the basis of the investigator administering treatment.

Treatment assignments will be masked to study subjects. Any non-study eye may receive any standard treatment at the discretion of the Investigator.

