8.2. Secondary Utilization Endpoints and Analysis

Secondary endpoints include:

- Clarity of the instructions for use, as assessed by the Investigator (yes, no)
- Differences between observed procedure and instructions for use, as assessed by an Observer (yes, no)

These secondary utilization endpoints will be analyzed employing descriptive statistics. Additionally descriptive statistics for other items on the investigator and observer questionnaires will be presented.

9. Safety Analysis

Safety analyses will be performed by treatment group for the Safety population at Day 7 and Month 12. Descriptive statistics will be used in safety analyses. Summary at the subject level will also be provided.

Non-treated randomized eyes and non-study eyes will only have all safety data listed. Adverse events will be summarized for these eyes, but otherwise they will not be included in safety tabulations.

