9.1.1. Incidence of Adverse Events

Summaries of the total number of ocular TEAEs and the number and percentage of eyes having at least one ocular TEAE will be provided by treatment group and for all treated eyes. Similarly, summaries of the total number of non-ocular TEAEs and the number and percentage of subjects having at least one non-ocular TEAE will be provided by treatment group. Ocular events and non-ocular events will be also summarized at the subject level for all subjects. Ocular events which occur in non-treated eyes and ocular events which occur in the second treated eye with a start date on or after the date of treatment in the first study eye but before the date of treatment in the second eye will be summarized separately as noted in section 9.1.10.

Ocular and non-ocular TEAEs will be summarized by SOC and PT. At each level of summarization, eye or subject level, an eye or subject is counted once for multiple events within PT/SOC.

Summaries by treatment group and for all treated eyes will be based on the number of treated eyes; therefore non-ocular events for subjects who have both eyes treated may be counted more

than once, "repeating" and counting the adverse event once for each treated eye. A non-ocular event will be counted for a given eye if the event start date is on or after the treatment date in the given eye. (i.e., non-ocular events which occur on or after the date of treatment in the first treated eye but before the date of treatment in the second eye will be counted once for the first eye only. If the event start date was on or after the treatment date in the second treated eye, the event would be counted twice, once for each eye.) Ocular events will be counted for a given study eye/treatment if the event start date is on or after treatment date within the given treated eye. Percentages will be calculated out of the number of treated eyes in the Safety Population.

Subject level summaries for all subjects will be based on the number of subjects who have at least one treated eye and a subject will be counted as having an event in the total subject summary if the subject has an event in at least one treated eye. Percentages will be calculated out of the number of subjects in the Safety Population with at least one treated eye.

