9.5. Vital Sign Measurements

Summary tables will be presented for vital sign data, including sitting systolic blood pressure (mmHg), sitting diastolic blood pressure (mmHg) and pulse rate (bpm), by treatment group and all subjects for the Safety population. Observed results at each visit and changes from baseline to each scheduled post-baseline visit will be presented.

Summaries by treatment group will be based on the number of treated eyes; therefore non-ocular vital sign assessments for subjects who have both eyes treated will be included more than once, "repeating" and including the assessments once for each treated eye.

All vital sign data will be presented in a listing.

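### In the Day 7 by-inserter tables, a second eye's non-ocular TEAEs are counted from its own injection but cut off on the first eye's clock, so it has 7 down to 1 countable days against 10 for a first eye

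*SAP*

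**What the plan says.** Four SAP rules and one protocol rule meet here.

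- **Clock.** SAP Section 4: "Study day for non-ocular events and assessments will be determined using the date of treatment in the first treated study eye". A treated second eye has its own clock for ocular assessments, but there is no equivalent for systemic data.
- **Cut-off.** SAP Section 4: "The Day 7 analysis will include all assessments with a start day on or before the upper limit of the Day 7 visit" window, which the SAP gives as study day 10.
- **Counting.** SAP 9.1.1: "A non-ocular event will be counted for a given eye if the event start date is on or after the treatment date in" that eye. An event starting after both eyes are treated is counted once under each. For the denominator: "Percentages will be calculated out of the number of treated eyes in the Safety Population".
- **Output.** SAP Section 9: "Safety analyses will be performed by treatment group for the Safety population at Day 7 and Month 12".
- **Second-eye timing.** Protocol 9.7.1 allows randomization of the second eye from the first eye's Day 7 visit "and no later than the last day of the study Day 7 visit window" of that first eye.

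All-subjects tables are separate: "Subject level summaries for all subjects will be based on the number of subjects who have at least one treated eye". For vital signs by treatment group, SAP 9.5 says that "non-ocular vital sign assessments for subjects who have both eyes treated will be included more than once", once per treated eye. These assessments also run on the first-eye clock.

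**The concern.** For a second eye, counting starts on one clock and stops on another. The eye enters the non-ocular count at its own injection and leaves it at first-eye day 10, which may be the same day. It still adds a full eye to its inserter's denominator. One percentage therefore pools eyes with unequal follow-up, and nothing in the SAP re-bases or exempts the second eye.

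The tables concerned fall within the stated aims. The primary objective (SAP 2.1) covers insert safety through 7 days, SAP 3.2 includes systemic adverse events through Day 7, and Protocol 14.3.6 assesses systemic safety by treatment group. Protocol 14.3.3 also holds the first analysis until all eyes have completed Day 7 or discontinued, so the cut sets aside second-eye follow-up that will already be in hand.

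**Working it through.** **Inputs.** The Day 7 window is ±3 days (Protocol 9.5; SAP Section 4), so it runs from 7 − 3 = day 4 to 7 + 3 = day 10. This reproduces the SAP's cut-off of study day 10. By Protocol 9.7.1, and assuming injection on the day of randomization as in the schedule, the second eye is injected on first-eye day d = 4 to 10. Protocol 7.2 plans about 30 eyes in about 25 subjects, from which I infer 30 − 25 = 5 second eyes.

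**Days counted per second eye.** Own day o falls on first-eye day d + o − 1. It is counted only if d + o − 1 ≤ 10, that is, o ≤ 11 − d. A first eye has 10 countable days.

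| d | Own days 1–10 counted (11 − d) | Own days 1–7 counted, min(7, 11 − d) | Own days 1–7 lost |
|---|---|---|---|
| 4 | 7 | 7 | 0 (0%) |
| 5 | 6 | 6 | 1 (14.3%) |
| 6 | 5 | 5 | 2 (28.6%) |
| 7 | 4 | 4 | 3 (42.9%) |
| 8 | 3 | 3 | 4 (57.1%) |
| 9 | 2 | 2 | 5 (71.4%) |
| 10 | 1 | 1 | 6 (85.7%) |

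**Across the trial.** Planned eye-days 1–7 are 30 × 7 = 210. With n second eyes all injected on day d, n × (d − 4) are lost. The number of second eyes is not stated, so a range is shown.

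| n | d = 4 | d = 7 | d = 10 |
|---|---|---|---|
| 3 | 0 | 9/210 = 4.3% | 18/210 = 8.6% |
| 5 | 0 | 15/210 = 7.1% | 30/210 = 14.3% |
| 8 | 0 | 24/210 = 11.4% | 48/210 = 22.9% |

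The right-hand column requires every second eye to be injected on the last permitted day.

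**Vital signs.** Let d and the second eye's own Day 7 visit day each run from 4 to 10, giving 7 × 7 = 49 combinations. The visit falls on first-eye day 10 or earlier in 10, on days 11–13 (in no analysis window) in 18, and on day 14 or later (past the Day 7 window) in 21. So in 18 + 21 = 39 of 49 it misses the Day 7 window. The scheduled Day 7 value repeated under the second eye is then a reading from before that eye's injection, since Protocol 9.7.2 takes vital signs before administration. In the other 10, two scheduled visits can share the window, a case that the selection rules in SAP Section 4 do not cover. These are combinations, not probabilities.

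**The case against.** **The cut-off is worded for assessments.** SAP Section 4 names events and assessments separately when it sets the clock, but only assessments when it sets the cut. This stands as a caveat: applying the cut to TEAEs is a reading, not an explicit rule. It is the natural one, because a start day suits adverse events and no other Day 7 cut for them is given. If it is wrong, the Day 7 cut for adverse events is undefined and still needs a sentence.

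**SAP 9.1.9 mitigates.** It reviews adverse events with onset within 7 days of the insert procedure, without restriction to ocular events, and tabulates those judged related to the injection. That anchor is the procedure, not first-eye study day. The Day 7 run may still be truncated, but the Month 12 analysis includes all data. This stands and reduces the consequence.

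**A systemic event belongs to the subject.** Once both eyes are treated it cannot be assigned to one inserter. SAP 3.2 defines the Day 1–Day 7 inserter evaluation on ocular events and places systemic events under the insert. This is a good reason to keep the first-eye anchor at subject level. It does not justify eye-level percentages with unequal windows.

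**Stronger readings the documents do not support.** A reader might infer that second-eye events are undercounted or that the inserter comparison is biased. The figures above are eye-days, no event rate is given, and an event after the second injection but by day 10 is counted under both eyes, so no net deficit is shown. Second eyes are also randomized independently (Protocol 7.1) at the same 2:1 ratio, so the design does not direct the shortfall to one inserter, although a handful of eyes could split unevenly. A reader might also infer that re-basing vital signs would make them inserter-specific. With the baseline left before the first insertion, second-eye changes would still span both insertions.

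**Conclusion.** The point holds as a minor, descriptive defect. Under the reading stated, a second eye has 7 down to 1 countable days for non-ocular TEAEs where a first eye has 10, under a common denominator. Over own days 1–7 the loss per second eye is 0% at d = 4, 43% at d = 7 and 86% at d = 10. With about 5 second eyes of 30, that is 0%, 7.1% and 14.3% of planned eye-days.

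This rests on the day-10 cut covering TEAE onset, injection on the day of randomization, and a number of second eyes inferred from approximate enrolment figures.

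Ocular safety, the success rule in SAP 8.1.1, subject-level tables, Month 12 TEAE counts and the listings are unaffected.

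**What to change.** 1. For by-treatment (eye-level) rows of non-ocular TEAEs in the Day 7 analysis, apply the day-10 cut-off from the injection date of the eye under which the row is counted. State that the cut-off applies to TEAE onset. Each treated eye then has the same own days 1–10.
2. Keep the first-eye anchor for subject-level tables.
3. Footnote that the by-inserter and all-subjects Day 7 tables can differ. With d = 7, an event on the second eye's own day 7 is first-eye day 7 + 7 − 1 = 13: it enters the second eye's inserter column but neither the first eye's column nor the Day 7 all-subjects table. This is the small downside.
4. Do not re-base vital signs. Either footnote that a second eye's Day 7 value is on the first-eye clock, normally pre-dates that eye's injection and is not inserter-specific (saying which value is shown if two scheduled visits share the window), or present Day 7 vital signs at subject level only.
5. Separately, reconcile second-eye timing. SAP 4.2 refers to study Day 7 of the first eye with no upper limit, SAP 3.1 refers to the Day 7 visit, and Protocol 9.7.1 adds a latest day. Under the SAP 4.2 wording alone, an eye injected after first-eye day 10 would have no countable days.

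The cost is SAP wording, one derived onset-day variable per eye and table footnotes. No new data are needed.

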4.1. Sample Size

This study is not statistically powered to detect a difference between the Mk I and Mk II inserters for the proportion of satisfactory procedures.

With a sample size of 20 eyes in the Mk II inserter group, the 95%, two-sided confidence interval of satisfactory procedures in the Mk II inserter group will be no larger than 27.2% - 72.8% when the exact binomial method and a proportion of 10 satisfactory procedures out of 20 Mk II inserter procedures are employed. All other satisfactory procedure proportions for the Mk II inserter will result in two-sided, 95% confidence bounds that are narrower than that described above.

With a sample size of 10 eyes in the Mk I inserter group, the 95%, two-sided confidence interval of the satisfactory procedures proportion will be no larger than 18.7% - 81.3% when the exact binomial method and a satisfactory procedures proportion of 5 out of 10 are employed. All other satisfactory procedures proportions for the Mk I inserter will result in two-sided, 95% confidence bounds that are narrower than that described above.

These confidence bounds, based on eye, are thought to adequately characterize the ease of use and other performance characteristics of the two inserters being studied.

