7.2. Number of Subjects

A total enrollment of approximately 30 eyes is planned for this study. Enrollment of approximately 25 subjects is expected, and will continue until:

- at least 20 and 10 study eyes each have been treated using the Mk II and Mk I inserters, respectively, and
- at least 10 different investigators each have performed at least one administration procedure.

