14. DATA ANALYSES

14.1. Sample Size

With a sample size of 20 eyes in the Mk II inserter group, the 95%, two-sided confidence interval of the satisfactory procedures proportion will be no larger than 27.2% - 72.8% when the exact binomial method and a satisfactory procedures proportion of 10 out of 20 are employed.

All other satisfactory procedures proportions for the Mk II inserter will result in two-sided, 95% confidence bounds that are narrower than that described above.

With a sample size of 10 eyes in the Mk II inserter group, the 95%, two-sided confidence interval of the satisfactory procedures proportion will be no larger than 18.7% - 81.3% when the exact binomial method and a satisfactory procedures proportion of 5 out of 10 are employed. All other satisfactory procedures proportions for the Mk I inserter will result in two-sided, 95% confidence bounds that are narrower than that described above.

These confidence bounds, based on eye, are thought to adequately characterize the ease of use and other performance characteristics of the two inserters being studied.

The study will continue until at least 20 Mk II and 10 Mk I inserter attempts have been randomized and performed, and at least 10 different investigators have attempted at least one administration procedure.

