4.2. Designation of Study Eye(s) and Randomization

For subjects with unilateral uveitis, the study eye will be the affected eye. For subjects with bilateral uveitis, the study eye(s) will be the eye(s) meeting eligibility criteria. If both eyes satisfy eligibility criteria, both eyes may be enrolled in the study. In a subject with both eyes eligible for enrollment, randomization of the subject's second study eye may occur no sooner than study Day 7 of that subject's first study eye.

Following confirmation of eligibility at Day 1, eyes will be randomly assigned (2:1) to receive the FAI insert using either the Mk II inserter or the Mk I inserter, respectively. Randomization assignments will be administered through a central Interactive Web Response System (IWRS). Randomization will be stratified on the basis of the investigator administering the treatment. The randomization schedule will be prepared using a blocked randomization and will be generated by an independent statistician. Only those subjects who have been enrolled in the study will have data recorded on the electronic case report forms (eCRF).

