8.1. Primary Utilization Endpoint

The primary utilization endpoint is defined as the proportion of intravitreal insertion procedures that are assessed by the Investigator as satisfactory. A satisfactory procedure is defined as one receiving a score from the Investigator as either Very Easy (VE), Easy (E), or Routine (R), according to the following categories:

- Very Easy (VE)
- Easy (E)
- Routine (R)
- Difficult (D)
- Very Difficult (VD)

If more than one inserter is used for the same eye, the results from the first inserter will be used for completing the questionnaires and analysis. Comments related to the second inserter will be presented in a listing. Any injector which penetrates the eye but does not deliver the FAI insert into the eye will be scored as Very Difficult for analysis.

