8.1.1. Primary Utilization Analysis

The primary utilization analysis will compare the proportion of intravitreal insertion procedures that are assessed by the Investigator as satisfactory (i.e., VE, E or R), in the Mk I inserter and the Mk II inserter groups.

The number and percentage of eyes with satisfactory intravitreal insertion procedures will be presented, for the Mk I inserter and the Mk II inserter groups of eyes employing descriptive statistics including 95% confidence intervals using the exact binomial methodology. The difference in proportions, the 95% exact unconditional confidence interval for the treatment difference (Mk II vs Mk I) in proportions, and the Fisher's exact test p-value will also be provided, however this comparison is considered exploratory only as the study is not powered to detect a difference between the inserters.

The primary utilization analysis will be conducted after all eyes in the study have completed study Day 7 or have discontinued study participation.

The study will be deemed a success for the Mk II inserter if the following condition is met: The proportion of Mk II procedures scored as satisfactory is not numerically lower than the corresponding proportion of Mk I procedures.

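### Do the exact binomial intervals for satisfactory procedures need adjusting because a small number of investigators rate their own procedures?

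*SAP*

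**What the plan says.** The primary endpoint is the proportion of insertions that the treating investigator scores as very easy, easy or routine (SAP 8.1). SAP 8.1.1 and Protocol 14.3.4.1 present it for each inserter "employing descriptive statistics including 95% confidence intervals using the exact binomial methodology". The same intervals are the sample-size rationale in SAP 4.1 and Protocol 14.1, where the plan says "These confidence bounds, based on eye, are thought to adequately characterize the ease of use".

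Three features bear on independence:

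- Enrolment continues until "at least 10 different investigators have attempted at least one administration procedure" (Protocol 14.1). I found no maximum per investigator.
- About 30 eyes are planned, and "Enrollment of approximately 25 subjects is expected" (Protocol 7.2). SAP section 4 accepts that "The same subject may be included more than once in the same treatment group if both eyes are randomized to the same inserter".
- "Randomization will be stratified on the basis of the investigator administering the treatment" (SAP 4.2), but investigator does not enter the analysis.

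SAP 8.1.1 adds a difference with an exact unconditional interval and Fisher's test, with the caveat that "this comparison is considered exploratory only as the study is not powered to detect a difference between the inserters". Success requires only that the Mk II proportion not be numerically below the Mk I proportion.

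**The concern.** A rating of one's own procedure carries the rater's skill and habits. Two Mk II procedures by one investigator are likely to be scored more alike than two by different investigators, and two eyes of one patient may share anatomy that makes insertion easy or hard. Positive correlation makes the Mk II total more variable than a binomial count, so a nominal 95% interval covers less often than stated. Neither document says that independence is assumed, gives a design effect or plans a sensitivity interval. Because the study is not powered for a difference, interval width is its only stated precision argument. At stake is whether a reader takes the Mk II estimate as more precise than it is.

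**Working it through.** **Inputs from the documents.** 20 Mk II and 10 Mk I eyes; two-sided 95% exact binomial intervals; at least 10 investigators; about 25 subjects for about 30 eyes.

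**Assumed, because the documents give neither.** The intra-investigator correlation (ICC) and the Mk II eyes per investigator. Scores are taken as beta-binomial within investigator, and the Mk II total is held at 20.

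**1. The plan's own figures.** The exact limits are the 2.5% point of Beta(x, n-x+1) and the 97.5% point of Beta(x+1, n-x). For 10/20 they are 27.2% and 72.8%; for 5/10 they are 18.7% and 81.3%. Both match.

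**2. Coverage with independent eyes.** Coverage is the sum of P(X = x) over the counts whose interval contains the true rate p. At p = 0.5 and n = 20 these are x = 6 to 14: the interval at 5/20 is 8.7-49.1% and misses, while at 6/20 it is 11.9-54.3% and covers. Each tail has probability 0.0207, so coverage is 1 - 2 x 0.0207 = 95.9%. The exact method therefore starts slightly above 95%.

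**3. Coverage with correlated scores.** The investigators' beta-binomial distributions are convolved to give the total. With 10 investigators x 2 eyes and ICC 0.2, each tail rises to 0.0318, so coverage is 1 - 2 x 0.0318 = 93.6%. Results for the Mk II interval, each pair at ICC 0.2 / 0.4:

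| Mk II eyes per investigator | p = 50% | p = 80% | p = 90% |
|---|---|---|---|
| 10 investigators, 2 each | 93.6 / 91.3% | 96.4 / 94.5% | 98.0 / 97.2% |
| 10 investigators: 6, 4, 2, 2, six with 1 | 90.6 / 84.9% | 94.4 / 90.5% | 96.6 / 94.3% |
| 15 investigators: five with 2, ten with 1 | 94.8 / 93.6% | 97.2 / 96.4% | 98.4 / 98.0% |
| 20 investigators, 1 each | 95.9 / 95.9% | 97.8 / 97.8% | 98.9 / 98.9% |

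**4. The same effect as width.** The design effect is 1 + (sum of m² / 20 - 1) x ICC, where m is an investigator's number of Mk II eyes, and the effective n is 20 divided by it.

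- Even loads: sum of m² / 20 = 40/20 = 2. At ICC 0.2 the design effect is 1.20, effective n is 16.7, and the widest interval is 25.1-74.9%.
- Uneven loads: (36 + 16 + 4 + 4 + 6)/20 = 3.3. At ICC 0.4 the design effect is 1 + 2.3 x 0.4 = 1.92, effective n is 10.4, and the interval is 19.2-80.8%.

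**5. Two eyes of one subject.** About 30 - 25 = 5 subjects contribute both eyes. If second eyes are allocated independently, 5 x (2/3)² = 2.2 pairs are expected to be both Mk II. Three such pairs with a fellow-eye correlation of 0.3 give 94.9% at p = 50%, which is negligible.

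**6. Mk I.** Independent-eye coverage at p = 50% with 10 eyes is 97.9%. A split of 3, 2 and five with 1 gives 96.7% / 95.4% at ICC 0.2 / 0.4.

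**7. Would an adjusted interval help?** Take the exact interval on the effective n, with the ICC fixed in advance. With even loads, a true rate of 80% and a true ICC of 0.4, assuming an ICC of 0.2 leaves coverage at 94.5%, the unadjusted value in the table. Assuming 0.4 gives 99.0%. The answer depends on a number for which the documents offer no source.

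**The case for a change.** The best case for a change is that interval width is the plan's only sample-size argument, so its main assumption ought to be stated and tested. The sponsor thought investigators mattered enough to stratify on them, and ten investigators is a minimum with no limit on individual loads. In an extreme layout, with one investigator treating 11 Mk II eyes and nine treating one each, coverage at a 50% rate and ICC 0.2 is 82.6%. Holding the total at 20 eyes, even 15 investigators do not restore 95% at a 50% rate.

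The direction of the effect stands, and so does its possible size under heavy concentration. The need for a new analysis does not follow. The larger losses require a substantial ICC, uneven loads and a true rate near 50% together. That rate is where the plan places its widest interval, not a rate it predicts, and the satisfactory category includes routine procedures. Estimating an ICC from about 10 very small clusters would be unstable, and fixing one in advance would be arbitrary. For the difference between inserters even the direction is unclear: a tendency that an investigator carries to both devices makes the planned interval too wide, and a device-specific tendency makes it too narrow.

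**Conclusion.** The conditional claim is true, and no change to the plan follows. With 20 Mk II eyes and assumed ICCs of 0.2 to 0.4, the shortfall from 95% at a 50% satisfactory rate is about 1 to 4 percentage points for evenly loaded investigators and about 4 to 10 points for the uneven split tabulated. At a 90% rate it is at most about 1 point in those layouts; stronger concentration would be worse. All of this rests on assumed correlations and loads.

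No decision depends on the coverage. The success rule uses point estimates and claims no error rate, the analysis is descriptive, and the inserter comparison is exploratory. The eye is openly named as the unit of analysis, and choosing the exact binomial method already implies independence. Because investigator is the randomization stratum, analysts can count eyes per investigator by inserter when they report, and note that the intervals assume independent eyes. An adjusted interval built on an arbitrary correlation would change no estimate or conclusion.
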